2. SYNOPSIS

Name of Sponsor: National Highway Transportation Safety Administration (hereafter referred to as NHTSA)
Name of Study Drug: Cannabis
Name of Active Ingredient: Bulk cannabis (6.18% THC/ <0.025% CBD) in a 500mg dose providing 30.9 mg THC
Title of Study: Validation of the Drug Impaired Driving Scenario (DIDS) On the CRCDS-Mini-Sim: Evaluating Sensitivity To The Effects of Cannabis and Alprazolam Protocol
Number of Sites and Study Location: This study will take place at 1 site in the US. NADS, University of Iowa, Iowa City, IA.
Phase of Development: 1
Planned Duration of Participation: Approximately 42 days, including up to 14 days for Screening, 2 days in each of 3 treatment periods, each separated by at least a 7-day washout period, and a follow-up phone call approximately 7 days after discharge from the final dosing period
Objectives: Primary: The primary objective of this study is to validate the Drug Impaired Driving Scenario (DIDS) using the CRCDS-2 driving simulator, by assessing the acute effects of cannabis relative to placebo on simulated driving performance. Assay sensitivity will be demonstrated by the significant effect of alprazolam 0.75 mg on driving and cognitive endpoints. Other: 
• A secondary objective to assess the effects of cannabis on cognitive and psychomotor functioning relative to placebo• Another objective is to evaluate the potential relationship between cannabis blood concentration and driving performance endpoints
Endpoints: Key Endpoint: 
• Standard Deviation of Lateral Position (SDLP) Other Key Endpoints: 
• Driving Performance Endpoints
○ Lane exceedance; including number, maximum duration, and area of exceedance○ Excessive speed count○ Average speed and speed deviation○ Excessive A_y (cornering speed threshold exceeded) and Total Crashes○ Divided Attention: Correct Responses, Omission Errors, Commission Errors, Reaction Time, Standard Deviation of Reaction Time○ Traffic light violations

- Gap decision making performance
 - Response to Crash Likely Events
 - Attention to mirrors task
 - Working memory task
 - Coherence
- CogScreen Symbol Digit Coding Test
 - Number of correct responses
 - Response Accuracy
 - Standard deviation of reaction time
- CogScreen Symbol Digit Coding – Immediate Recall
 - Immediate recall accuracy
- CogScreen Symbol Digit Coding – Delayed Recall
 - Delayed recall accuracy
- CogScreen Visual Sequence Comparison Test
 - Response speed
 - Response Accuracy
 - Standard deviation of reaction time
- CogScreen Divided Attention Test
 - Response speed
 - Number of premature responses
 - Response accuracy
 - Lapses
 - Multitasking scores
- CogScreen Matching To Sample Test
 - Response speed
 - Response accuracy
 - Standard deviation of reaction time
- CogScreen Pathfinder Number
 - Response speed
 - Response accuracy
 - Response coordination
- CogScreen Shifting Attention Test
 - Response speed
 - Response accuracy
 - Standard deviation of reaction time
- CogScreen Dual Task Test
 - Tracking errors
 - Number of boundary hits
 - Previous number response speed
 - Previous number response accuracy

- Previous number standard deviation of reaction time
- Multitasking scores
- Test of Variables of Attention (TOVA)
 - Response time variability (by quarter and overall)
 - Response speed (by quarter and overall)
 - Commission errors (by quarter and overall)
 - Omission errors (by quarter and overall)
- Self-reported readiness to drive (“Right now do you feel safe to drive?” [Yes/No])
- VAS to assess subject’s motivation and self-appraisal of their driving performance
- Other self-report measures

Other:

- Changes from baseline in vital signs, clinical laboratory data, ECG parameters, and suicidal ideation and behavior using the Columbia Suicide Severity Rating Scale (C-SSRS)
- Relationship between blood concentration of THC and SDLP or other driving or cognition endpoints

Study Description:

This randomized, double-blind, active- and placebo-controlled, 3-arm, 3-period crossover study is designed to validate the DIDS scenarios using the CRCDS-2 driving simulator by assessing the acute effects of cannabis relative to placebo on simulated driving performance. Assay sensitivity will be demonstrated by the significant effect of alprazolam 0.75 mg on driving and cognitive endpoints.

Following a screening/training period of up to 14 days, eligible subjects will be admitted to NADS on Day 1 of Period 1. Baseline performance for cognitive testing will be obtained and subjects will practice the CRCDS2-MiniSim driving simulator, then they will be taken to a supervised off-site residential facility from the end of Day 1 procedures until the start of procedures on Day 2. Subjects will be randomized 1:1:1 into one of 6 treatment sequences as shown in [the table below](#) on Day 1. Study drug will be administered by inhalation on Day 2 (first subject dosed at approximately 08:40); precise timing is relative, as subject dosing will be staggered/offset to accommodate staffing and subject flow. Blood samples for pharmacokinetic analysis will be drawn pre-dose and again 40 minutes post-dose and 3.25 hours post-dose. Symbol Digit Coding (SDC), Pathfinder Number (PFN), Readiness to Drive Question, and the Karolinska Sleepiness Scale (KSS) will be administered approximately 30 minutes post-dose. Driving assessments will begin approximately 45 minutes following dosing (i.e., at approximately 09:25). Driving performance will be assessed via the approximate 1-hour Drug Impaired Driving Scenario (DIDS), on the CRCDS2-MiniSim driving simulator, comprised of suburban, urban and highway driving tasks. The scenario includes challenges designed to assess lane position control, speed control, safety awareness and responsibility, driving-related decision making, multitasking, and vigilance. Immediately after completing the driving simulation, subjects will be administered the visual analog scales, or VAS, followed by the cognitive test battery (SDC, Visual Sequence Comparison [VSC], Divided Attention Test – Dual [DAT-Dual], PFN, SDC Delayed Recall [SDCDR], Shifting Attention Test – Instruction, Matching to Sample [MTS], Dual Task Test – Combined [DT Combined], and Test of Variables of Attention [TOVA]). At approximately 3.5 hours post-dose the cognitive test battery (i.e., SDC, VSC, DAT-Dual, PFN, SDCDR, SAT Instruction, MTS, DT Combined, TOVA) and self-report measures will be repeated.

[figure not shown]
Subjects will undergo initial driving simulator training and practice during the Screening period and will complete a practice drive on Day 1 of each treatment period.

Subjects will be discharged from NADS on the afternoon of Day 2 of each period approximately 5.33 hours post-dose, provided they are medically stable for discharge in the opinion of the Investigator based on the criteria established by the medical monitor. The subject will not be able to drive themselves home and will have transportation arranged.

After a washout of at least 7 days and no more than 10 days between administration of the last dose in one period and administration of the first dose in the next period, subjects will be readmitted to NADS on Day 1 of Period 2 and receive study drug according to the assigned treatment schedule. All study assessments will remain the same as in Period 1. The same process will be repeated for Period 3.

Seven days (± 2 days) after discharge from Period 3, subjects will receive a follow-up/end-of-study phone call from the site to evaluate the presence of any AEs and collect any new concomitant medication/procedure information.

Figure 1. Study Design

The schedule of assessments is provided in [Table 1](#).

The following regimens will be assessed:

- Treatment A: cannabis (inhaled)
- Treatment B: alprazolam 0.75 mg PO
- Treatment C: placebo PO
- Subjects receive 1 tablet of alprazolam and/or matched placebo 40 minutes prior to administration of inhaled cannabis/or matching placebo on Day 2 of each treatment period.

Treatment Sequences

Sequence	1	2	3
1	A	B	C
2	B	C	A
3	C	A	B
4	A	C	B
5	B	A	C
6	C	B	A

Number of Subjects (planned): Approximately 12 subjects will be randomized and dosed to target 6 - 8 subjects completing the 3 treatments. Efforts will be made to randomize an approximately equal number of subjects by gender. Efforts will be made to randomize an approximately equal number of “low frequency” users (1-10 uses per month) and “high frequency” users (>20 uses per month).

Eligibility Criteria:

Inclusion

1. Subject understands and provides written informed consent prior to the initiation of any protocol-specific procedures.
2. Subject is able to comprehend and willing to comply with the requirements of the protocol.
3. Subject is a healthy male or female, 19 to 45 years of age, inclusive, at Screening.
4. Subject has a regular sleep pattern (usual bedtime between 21:00 and 00:00).
5. Subject has Score <10 on Epworth Sleepiness Scale at Screening.
6. Subject is able to reliably perform study assessments at Screening (On practice drive, SDLP no higher than 1 standard deviation greater than the mean for normal healthy adults completing the practice scenario; subject exhibits ≥ 11 instances of lane exceedance; or subject has fewer than 7 correct hits on the Divided Attention task; CogScreen SDC Correct no less than 1 standard deviation below the mean for healthy adults); demonstrates the ability to understand task instructions at Screening; and is physically (e.g., adequate manual dexterity, vision, and hearing) and cognitively capable of performing study tasks at Screening.
7. Subject possesses (and is willing to provide) a valid driver’s license and is an active driver (minimum of approximately 3,000 miles per year for the previous 3 years).
8. Subject is determined to be (by self-report) either an infrequent user of cannabis (i.e., 1-10 uses per month) or a frequent user of cannabis (i.e., >20 uses per month) over the preceding 90 days.

9. Subject is willing to abstain from cannabis use (other than study drug) beginning 7 days prior to admission for the first treatment period (Day 1) until discharge from the facility on Day 2 of period 3.
10. Female subjects must meet one of the following criteria: 1) If of childbearing potential, female subjects agree to use two contraceptive regimens or remain abstinent during the study; or 2) if of non-childbearing potential, female subjects should be surgically sterile or in a menopausal state.

Exclusion

11. Subject has a significant history and/or presence of hepatic, renal, cardiovascular, pulmonary, neurological, psychiatric, gastrointestinal, hematological, immunologic, ophthalmologic, metabolic, or oncological disease, or any other medical issue that would, in the opinion of the Investigator, present undue risk for the subject in the study.
12. Subject has a history of suicidal behavior within 24 months of Screening, has answered YES to questions 3, 4, or 5 on the C-SSRS at Screening or at any clinic admission, or is currently at risk of suicide in the opinion of an Investigator.
13. Subject has a recent history (within 6 months prior to Screening) of substance use disorder (including alcohol) (as judged by the Investigator) or regularly consumes >2 alcoholic drinks/day during the last 3 months prior to Screening (1 alcoholic drink is approximately equivalent to: beer [284 mL], wine [125 mL/4 ounces], or distilled spirits [25 mL/1 ounce]). Subjects who consume up to 3 drinks per day but less than 14 drinks per week may be enrolled at the discretion of the Investigator.
14. Subject demonstrates simulator sickness questionnaire scores which are indicative of simulator sickness as defined in the driving simulation operations manual.
15. Subject regularly consumes excessive amounts of caffeine, defined as greater than 6 servings (1 serving is approximately equivalent to 120 mg of caffeine) of coffee, tea, cola, or other caffeinated beverages per day.
16. Subject smokes more than 10 cigarettes or e-cigarettes, or 3 cigars or pipes per day, or is unable to refrain from smoking during study visits.
17. Subject has been exposed to an investigational drug or device within the 30 days, or 5 half-lives (if known), whichever is longer, prior to Screening.
18. Subject has used a prescription or over-the-counter medication known to cause sedation within 7 days prior to Admission for Period 1 and is unwilling or unable to refrain from sedating medication use during study participation.
19. Subject has used any benzodiazepine, barbiturate, or GABA_A modulator (e.g., eszopiclone, zopiclone, zaleplon, and zolpidem) within 28 days prior to Admission for Period 1 or is unwilling or unable to refrain from medication use during study participation.
20. Subject has a history of hepatitis B surface antigen, hepatitis C antibodies, or human immunodeficiency virus (HIV) antibodies 1 or 2.
21. Subject is pregnant or breastfeeding at Screening or any clinic admission or will attempt to become pregnant at any time during study participation.
22. Subject has a clinically significant abnormal finding on 6-lead electrocardiogram (ECG) at Screening or at any clinic admission. The ECG may be repeated once for confirmatory purposes if initial values obtained exceed the limits specified.
23. Subject has a positive urine test for drugs of abuse (other than tetrahydrocannabinol [THC]) or has a BrAC >0.0 at Screening or any admission.
24. Subject has any clinically significant abnormal physical examination finding at Screening or any clinic admission.

- 25. Subject participates in night shift work.
- 26. Subject has traveled across ≥ 1 time zone in the 2 weeks prior to Admission for Period 1 or is expected to travel across ≥ 1 time zone during the study.
- 27. Subject is investigative site personnel or their immediate families (spouse, parent, child, or sibling whether biological or legally adopted).

Study Drug Dosage and Mode of Administration: Cannabis will be administered by inhalation.

Reference Therapy, Dosage and Mode of Administration:

Alprazolam (active comparator) at a dose of 0.75 mg will be administered orally.

Cannabis matching placebo will be administered by inhalation.

Alprazolam matched placebo will be administered orally.

Duration of Treatment:

Subjects will receive 1 500 mg dose of cannabis active on Day 2 of one of the three periods.

Subjects will receive 1 dose of alprazolam 0.75 mg active on Day 2 of one of the three periods.

Subjects will receive placebo in all treatments.

Subjects will not receive active cannabis and alprazolam during the same period.

Statistical Methods:

A statistical analysis plan (SAP) will provide a detailed description of the analyses to be performed in the study. The SAP will be finalized and approved prior to database lock. Any deviations from or changes to the SAP following database lock will be described in detail in the clinical study report.

Analysis Sets

Randomized Set: All subjects who are randomized

Full Analysis Set (FAS): all randomized and treated subjects that have at least one primary efficacy measure (SDLP) in any treatment period.

Safety Set (SS) will include all subjects administered at least one dose of any study drug.

PK Set will include subjects in the Safety Set who have at least one collected blood sample from which a valid blood concentration can be measured.

Primary analysis

The FAS will be used for the primary analysis.

The comparison of primary interest is cannabis versus placebo (Day 2) as a function of frequency of self-reported cannabis use. The statistical significance of alprazolam versus placebo ($p < 0.05$) comparison for SDLP is considered only to validate the experiment as having the ability to detect effects (i.e., assay sensitivity).

Formal statistical tests (when performed) will be 2-sided and tested at the $\alpha = 0.05$ level of significance.

Secondary Analyses

The FAS will be used for secondary analyses.

Safety Analyses

Safety and tolerability of cannabis will be assessed by the incidence of TEAEs, and by changes from baseline in vital signs, ECG parameters, and suicidal ideation and behavior using the C-SSRS.

Safety data will be listed by subject and summarized by treatment. All safety summaries will be performed on the SS.

PK Analyses

The potential relationship between THC blood concentration and SDLP or other driving or cognition endpoints will be examined using regression techniques.

Table 1: Schedule of Assessments

Event	Screening	Double-Blind Treatment Periods 1 through 3 ^a		
		Day 1 (Admission)	Day 2	Follow-up /or ET (phone) ^b
Informed consent	X			
Inclusion/exclusion	X	X		
Demographics	X			
Medical history	X			
Epworth Sleepiness Scale	X			
Body weight/height/BMI ^c	X			
Physical examination ^d (full)	X			
Physical examination ^d (brief)		X		
HIV and hepatitis screen	X			
Urine drug & breathalyzer alcohol screen	X	X		
Vital signs ^e	X	X		
C-SSRS ^f	X			
6-lead ECG	X			
Randomization		X ^g		
Screen and Familiarize DIDS on CRCDS2-MiniSim	X (Day -14 to -3)			
Simulator Sickness Questionnaire	X (Day -14 to -3)			
Screen on CogScreen Battery and TOVA ^h	X (Day -14 to -3)			
Practice CogScreen, TOVA, and DIDS on CRCDS2-MiniSim ⁱ		X		

Administer study drug ^j			X	
Blood PK collection ^k			X	
CogScreen Subtests ^l not found., 1			X	
TOVA ¹			X	
TBD Self-Report Scales			X	
Self-perceived safety to drive question ^m Error! Reference source not found.			X	
Drug Impaired Driving Scenario ^o Reference source not found.			X	
VAS ^m			X	
Discharge ⁿ			X	
Phone call				X
Adverse events/SAEs	Ongoing from the time of consent throughout the duration of study participation			
Prior/concomitant medications ^o	X			
CRCDS2 = Cognitive Research Corporation Driving Simulator-2 nd Edition; C-SSRS = Columbia Suicide Severity Rating Scale; DIDS = Drug Impaired Driving Scenario; ECG = electrocardiogram; ET = early termination; HIV = Human immunodeficiency virus; PK = pharmacokinetic, SAE = Serious adverse event; VAS = Visual Analog Scale				

^{3a}Subjects will be admitted to NADS on Day 1 of each treatment period and then housed at the supervised off site residential facility under NADS staff supervision between the end of procedures on Day 1 and start of procedures on Day 2. Each treatment period will be separated by a washout of at least 7 days and no more than 10 days between administration of the last dose in one period and administration of the first dose in the next period.

⁴Error! No bookmark name given. In the event of Early Termination, efforts should be made to obtain the safety assessments indicated for the day of discharge (Day 2).

^c Height and weight will be measured at Screening only.

^d A symptom-directed physical examination may be conducted at any time as needed.

^e Vital signs will include blood pressure, heart rate, respiratory rate, pulse oximetry, and temporal temperature (°F). Heart rate and blood pressure to be collected in supine position after the subject has been resting for approximately 3 minutes.

^f The “Baseline/Screening” C-SSRS form will be completed at Screening

^g Subjects will be randomized to a treatment sequence on Day 1 of Period 1.

ⁱ Subjects will complete a training and practice CogScreen session at Screening and will complete a practice CogScreen Session in the afternoon on Day 1. Subjects will complete a practice drive on the CRCDS2 at Screening and will also complete the practice drive on the afternoon of Day 1.

Error! Reference source not found. Oral (PO) study drug (alprazolam or placebo) will be administered approximately 40 minutes prior to Inhaled study drug (cannabis or placebo) according to the treatment sequence assigned at Period 1.

^k Three separate blood samples for PK analysis will be collected; the samples will be collected pre-dose on Day 2, at 40 minutes (± 5 minutes) post-dose (PPP-001) on Days 2 and at 3.25 hours (± 5 minutes) post-dose on Day 2.

Error! Reference source not found. Symbol Digit Coding, Pathfinder Number, KSS, and self-perception question will be completed prior to driving assessments. The KSS will also be administered pre-dose (cannabis).

Error! Reference source not found. CRCDS2-MiniSim drive to be completed in the morning of Day 2 starting approximately 45 minutes following dosing of cannabis. Upon completion of the drive subjects will complete the cognitive test battery and self-report questionnaires.

^m Visual analog scales to assess subject's motivation and self-appraisal of their driving performance immediately upon completion of the driving assessment. The cognitive test battery and self-report questionnaires will be repeated at approximately 3.5 hours post-dose (cannabis).

ⁿ Subjects will be discharged upon completion of Day 2 assessments if deemed medically stable for discharge by the Investigator.

^o Medications taken within 30 days of Screening and for the duration of the study will be recorded.

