PURPOSE OF PRESENT STUDY: The primary purpose of the current study is to establish a standardized protocol for assessing drug impaired driving. Validation of this methodology is to be accomplished with a study using cannabis, alprazolam, and matching placebo. As part of this research effort, investigators have worked to identify the driving tasks and cognitive abilities found to be most vulnerable to the impairing effects of cannabis. In addition, an effort was made to identify the subject characteristics associated with increased vulnerability to the impairing effects of cannabis. Worked was conducted to develop a methodology for determining when drivers are safe to resume driving after drug exposure. The current study is designed to test these hypotheses.

Simulated driving will be performed using an updated version of Cognitive Research Corporation's Driving Simulator (CRCDS2 MiniSim). The prior version of this simulator has been used in dozens of driving studies submitted for regulatory review. Driving performance will be assessed using an approximate 1-hour Drug Impaired Driving Scenario (DIDS), comprised of suburban, urban and highway driving tasks. The scenarios include challenges designed to assess lane position control, speed control, safety awareness and responsivity, driving-related decision making, multitasking, and vigilance. These domains correspond to the Essential Driving Ability

Domains described by Kay and Logan (2011). In addition, cognitive functions associated with driving performance and self-report measures will also be administered.

Consistent with the principles outlined in the FDA Guidance for Industry (2017), this study includes both a positive (active) and placebo control condition. The study is designed to assess the duration of drug effects. Readiness to resume driving will be assessed using both self-report and objective testing. Subjects will include regular (daily) users and weekly users of cannabis. The intent is to assess the impact of pattern of drug use on driving performance. A cross-over study design will be utilized to maximize statistical power.

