7.2. Number of Subjects

Approximately 12 subjects will be randomized and dosed. Efforts will be made to randomize an approximately equal number of male and female subjects. Efforts will be made to randomize an approximately equal number of “low frequency users” (i.e., 1 – 10 uses of cannabis per month) and “high frequency users” (i.e., > 20 uses of cannabis per month).

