9.5. Randomization and Blinding

This is a randomized, double-blind, active- and placebo-controlled study. On Day 1 of Period 1, subjects will be randomized 1:1:1 into one of 6 treatment sequences (

Table 3). The active and placebo treatments are identical in appearance within each group and matched placebo will be administered as necessary to maintain the blind ([Table 4](#)).

The allocation to treatment sequence will be based on a randomization schedule generated by blinded study personnel. The randomization schedule will be kept strictly confidential, accessible only to authorized personnel until the time of unblinding. A copy of each randomization schedule will be held by the Study Pharmacist.

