13.5. Pharmacodynamic Analyses

All PD analyses will use the FAS Set.

The FAS will be used for the primary analysis. Summary statistics will be provided (mean, standard deviation, median, minimum, maximum) for each treatment. Figures will be provided for the within-subject difference scores by treatment and day as both a histogram and scatter plot. Data listings for driving simulator data will be provided.

SDLP data will be analyzed using a mixed model for repeated measures (MMRM) with fixed effects for sequence, period, and treatment and random effect for subject. A log-transformation of SDLP values to obtain normal distribution of data will be considered, if necessary. An unstructured covariance structure and Kenward-Roger degrees of freedom will be used. In the event an unstructured covariance structure fails to converge, a variance components covariance structure will be assumed. In addition to treatment effect, p-values for significance testing of period and sequence effects will be provided. Pair-wise comparisons of differences in means and two-sided 95% CIs on differences will be provided for all active treatments versus the placebo treatment.

The comparison of primary interest is cannabis versus placebo on Day 2 as a function of frequency of self-reported cannabis use. The statistical significance of alprazolam versus placebo ($p < 0.05$) comparison for SDLP is considered only to validate the experiment and having the ability to detect effects (i.e., assay sensitivity).

Formal statistical tests (when performed) will be 2-sided and tested at the $\alpha=0.05$ level of significance. Cannabis will be considered non-inferior to placebo if the two-sided upper 95% confidence limit on the difference in SDLP between that dose and placebo is less than 4.4 cm, and it can be concluded that the effect of cannabis on driving is less than that seen at 0.05% BAC, which is a level associated with increased crash risk. No adjustment to alpha levels will be made for either the comparison of alprazolam to placebo, or for secondary endpoints or analyses.

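### Sex and cannabis-use frequency are targeted as two separate margins at randomisation, so the between-subject use-frequency comparison can be partly confounded with sex

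*Combined protocol and SAP*

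**What the plan says.** The Synopsis (Number of Subjects) states: "Approximately 12 subjects will be randomized and dosed to target 6 - 8 subjects completing the 3 treatments". Two recruitment aims follow. For sex: "Efforts will be made to randomize an approximately equal number of subjects by gender"; Section 7.2 repeats it as "Efforts will be made to randomize an approximately equal number of male and female subjects". For use frequency, a separate sentence in both places seeks similar numbers of low-frequency users (1-10 uses a month) and high-frequency users (more than 20). Both aims are efforts at approximate equality, both apply at randomisation, and neither refers to the other.

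Section 9.5 says "subjects will be randomized 1:1:1 into one of 6 treatment sequences" and names no stratification factor.

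Section 13.5 states: "The comparison of primary interest is cannabis versus placebo on Day 2 as a function of frequency of self-reported cannabis use". The Synopsis says the same, and Section 5.1 gives the purpose: "The intent is to assess the impact of pattern of drug use on driving performance". The SDLP model in Section 13.5 has fixed effects for sequence, period and treatment and a random subject effect. It has no term for sex or for use frequency.

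**The concern.** Each subject is their own control for cannabis against placebo. Whether that effect differs between low- and high-frequency users is another matter: it compares two groups of different people, and any characteristic distributed unevenly between them can contribute to the difference.

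The two targets do not prevent this for sex. Six men and six women, six low and six high users, is satisfied equally by 3 men and 3 women in each use group and by 5 men and 1 woman in one group against 1 man and 5 women in the other. Randomisation cannot help, because it assigns treatment sequences, whereas sex and use frequency come with the subject. Only recruitment controls their joint distribution.

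If the cannabis effect on SDLP differs by sex, part of that difference would be read as an effect of use pattern. By aiming for equal numbers of men and women, the plan already treats sex as worth balancing, but not within the groups being compared.

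**Working it through.** **Inputs.** About 12 randomised and 6-8 completers (Synopsis). The documents give no SD, effect size, power or dropout rate, so the planned number cannot be derived; it implies non-completion of 1 - 8/12 = 33% to 1 - 6/12 = 50%. Assumed here: margins of exactly 6/6 for sex and for use frequency, and, at first, independence of the two.

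**Sex split at randomisation.** Let k be the number of men among the 6 high-frequency users. Then P(k) = C(6,k) × C(6,6-k) / C(12,6), with C(12,6) = 924.

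| Split in a use group | Calculation | Probability |
|---|---|---|
| 3:3 | 400/924 | 43.3% |
| 4:2 either way | 2 × 225/924 | 48.7% |
| 5:1 either way | 2 × 36/924 | 7.8% |
| 6:0 either way | 2 × 1/924 | 0.2% |

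Not 3:3: 56.7%. 5:1 or worse: 8.0%.

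**If sex and use are associated.** Weight each count by OR^k. For an assumed odds ratio of 2 the weights for k = 0 to 6 are 1, 72, 900, 3200, 3600, 1152 and 64 (total 8989). P(not 3:3) = 1 - 3200/8989 = 64%, and P(5:1 or worse) = (1 + 72 + 1152 + 64)/8989 = 14%. For an assumed odds ratio of 3 the figures are 73% and 24%. The documents give no odds ratio.

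**Share of a sex difference passed on.** This is the difference in the proportion of men, k/6 - (6-k)/6.
- 4:2 versus 2:4: 4/6 - 2/6 = 1/3.
- 5:1 versus 1:5: 5/6 - 1/6 = 2/3.

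**Size beside the sampling error.** Work in units of the SD of the within-subject cannabis-placebo difference. With 6 against 6 the contrast has SE = √(1/6 + 1/6) = 0.58 SD and a 95% half-width of 1.29 SD. For an assumed sex difference of 0.5 SD, a 4:2 split shifts the contrast by 0.17 SD and a 5:1 split by 0.33 SD; for 1 SD, by 0.33 and 0.67 SD.

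Under independence the expected shift is zero. Var(k) = 6 × ½ × ½ × 6/11 = 0.818, so the share passed on, (k-3)/3, has variance 0.818/9 = 1/11. The overall SE is then multiplied by √[(1/3 + 0.25/11)/(1/3)] = 1.03 for 0.5 SD, and by √[(1/3 + 1/11)/(1/3)] = 1.13 for 1 SD.

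**Cost of adjusting for sex.** The correlation between sex and use group is 1/3 at 4:2 and 2/3 at 5:1. The variance inflation 1/(1 - r²) is 1/(1 - 1/9) = 1.125 and 1/(1 - 4/9) = 1.8, plus one degree of freedom.

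**Effect of crossing.** Three subjects per sex-by-use cell removes the imbalance at randomisation. Among 6, 7 and 8 completers, with dropout unrelated to either factor, simulation (200,000 draws) puts the chance that the groups' sex shares differ by 50 points or more at about 36%, 24% and 25% under separate targets, and 24%, 12% and 9% under crossing.

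**Completers per use group, equal dropout.** P(2 or fewer in a group) at 6 completers is 1 - 400/924 = 57%; at 7, 2 × (90 + 6)/792 = 24%; at 8, 2 × 15/495 = 6%. Crossing by sex does not alter these figures.

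**The case against.** The best case against acting is that the effect is small and speculative. Section 5.1 lists characteristics likely to interact with the drug as substance-use pattern, driving experience and age; sex is not among them. A fixed nominal dose acting through body weight is a weak route, since Section 10.5 leaves inhalation under the subject's control. Most imbalances would be 4:2, the mildest. Under independence the added error is about 3% of the SE for an assumed 0.5 SD sex difference, and even a perfect 3 versus 3 comparison has a 95% half-width of 2.27 SD. The missing frequency term in the Section 13.5 model is a larger obstacle to this comparison. All of this stands, and it limits the point to a modest improvement. It does not remove it: the imbalance is more likely than not, and if sex and use are associated the shift is no longer zero on average.

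A reader might infer that sex and use cannot be separated in 12 subjects. That is wrong: complete aliasing has a 0.2% chance under the stated assumptions, and adjustment stays possible at the variance costs shown.

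A reader might also infer that the comparison will rest on one or two completers in a group. That risk belongs mainly to the low end of the target (57%, 24% and 6% at 6, 7 and 8 completers). Moreover, the primary analysis uses the FAS (Section 13.1), which keeps anyone with one SDLP value. A subject missing only the alprazolam period still informs cannabis versus placebo, so more subjects than the completers may contribute. Nor do the documents show heavier dropout among frequent users: they give no rate by group, and willingness to abstain is an entry criterion for all (Section 8.1).

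**Conclusion.** The point holds in a limited form. Separate margins leave the use-frequency contrast open to partial confounding with sex: 57% of trials would be off 3:3 and 8% at 5:1 or worse, passing on one third and two thirds of any sex difference respectively. This rests on exact 6/6 margins and independence. The size of any sex difference, and of any sex-use association, is not in the documents and was assumed.

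It would be too strong to conclude that the main cannabis-placebo result is compromised. That effect is estimated within subjects and is untouched. Only the comparison across use groups is affected, and there the gain from crossing is modest.

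**What to change.** In the Synopsis and Section 7.2, replace the two separate targets with one joint target, for example: *Recruitment will aim for about three men and three women among the low-frequency users, and the same among the high-frequency users.* Keep the planned total of about 12, and direct later enrolment to the sex-by-use cell that is short.

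The cost is one reworded statement in two places and a simple recruitment tracker. The downside is slower filling of the hardest cell.

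A completer target per use group should not be presented as a guaranteed remedy. Once three subjects per cell have been randomised, no places remain within 12 to redirect. If completer counts are discussed, give all three figures (57%, 24% and 6%) with the equal-dropout assumption and the note on the FAS.
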